The null hypothesis for the primary endpoint is that there is no treatment difference between patients who receive tele-rehab-supported PT versus traditional home and/or clinic-based PT. The alternative hypothesis is that a treatment difference exists between patients who receive tele-rehab-supported PT versus traditional home and/or clinic-based PT.

Let μ_T and μ_C be the average total health care costs for the virtual and control PT groups, respectively. The null hypothesis and the alternative hypothesis will be as follows:

$$\begin{aligned} H_0: \mu_T &= \mu_C \\ H_A: \mu_T &\neq \mu_C \end{aligned}$$

The primary statistical method for the hypothesis test will be t-test, and the mean difference between groups will be presented with a 95% confidence interval (CI). The test is two-sided even though we are more interested in determining that the intervention group is superior to the control group to allow for a possible negative significant difference.

Let \bar{X}_T and \bar{X}_C be the sample mean costs for the virtual and control groups, respectively, and let S_T^2 and S_C^2 be the sample variance for the virtual and control samples, respectively. The equality of the variances of the two samples will be tested using the Folded F-test (i.e., $F = \text{Max}(S_T^2, S_C^2)/\text{min}(S_T^2, S_C^2)$). If there is not strong statistical evidence to say that the variances of the two samples are different (insignificant F-test and 4-fold variance difference), then the alternative hypothesis for total cost will be concluded when the associated t-test statistic assuming equal variance is less than the 2.5th percentile of the Student's t distribution with $n_T + n_C - 2$ degrees of freedom, where n_T is the number of subjects in the virtual group and n_C is the number of subjects in the control group. Otherwise, the t-test will be computed assuming the variances are unequal.

If a parametric method is determined not to be possible through normality checks (Shapiro-Wilks test) or transformations, a Wilcoxon rank-sum test will be performed for the primary effectiveness endpoint and a 95% CI for the median difference presented.

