6 OVERVIEW

6.1 Synopsis

This is a multi-center, randomized, clinical trial to evaluate the costs and clinical effectiveness of technology-supported home-based physical therapy (PT) compared with traditional PT in the home or clinic. Duke University and Duke Clinical Research Institute (DCRI), along with the sponsor, Reflexion Health, Inc., will be responsible for the design, implementation, and leadership of the VERITAS study. Data analysis and publications will be managed according to a written plan designed to maintain appropriate scientific oversight and rigor by the DCRI. A Data Monitoring Committee (DMC) will not be used.

This trial will include subjects scheduled for a total knee replacement (TKR), as defined by protocol inclusion and exclusion criteria. All subjects will receive standard of care as defined by current site-specific and local guidelines for the management of TKR.

A total of 300 randomized subjects are planned for this study. Subjects will be randomized in a 1:1 ratio, stratified by site, to receive either tele-rehab-supported PT or traditional home and/or clinic-based PT.

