9.3 Data from Multiple Sites

The VERITAS study is a multi-center clinical trial within sites in the United States. Approximately six orthopedic surgical practice groups will be selected to enroll patients in the trial. Sites will be identified and approached based on estimated surgery volume, and the availability of staff resources to support successful participation. Site selection will be limited geographically to a 50-mile radius around the Durham-Chapel Hill Comprehensive Joint Replacement (CJR) bundle region to minimize the variation of in-hospital costs. Site start-up may be staged to allow for controlled run-in of the first patients at each site.

The site where a subject was randomized is included as part of the randomization strata. Exploratory analyses will include assessing the influence of site on treatment effects for both the primary and secondary endpoints. This will be done by adding a fixed-effect main site effect and interaction term between randomization strata (site) and treatment in a generalized linear model used to analyze the primary and secondary endpoints. This is described in more detail in Section 9.12 of this document.

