9.9 Power and Sample Size Calculations

The primary aim of this study is to assess the difference in outpatient post-surgical costs between the control and intervention groups at 12-weeks post-operative. The exact post-procedure cost estimates under study are unknown; however, we can estimate that an effect size of approximately 0.33 can be detected with 150 subjects per group with at least 80% power. The effect size is the ratio of the mean difference over the standard deviation (SD) assumed for each population. Lower variability would enable detection of a smaller cost difference, or the detection of a larger difference with fewer patients. The sample size estimates were made assuming a two-sample t-test with equal variance and a significance level of 0.05. Thus, with 300 subjects we can detect an effect size of 0.33 which represents a whole scenario of cost differences that can be detected with at least 80% power that is dependent on the variability of the costs under study. The below table illustrates some example cost differences that could be detected based on the assumed SD of the costs.

Standard Deviation (SD)	Mean Cost Difference (\$)	Standard Deviation (SD)	Mean Cost Difference (\$)
100	32.50	800	259.60
200	64.90	900	292.10
300	97.40	1000	324.50
400	129.80	1100	357.00
500	162.30	1200	389.50
600	194.70	1300	421.90
700	227.20	1400	454.40
750	243.40	1500	486.80

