9.10 Primary Effectiveness Analysis

The total health service use costs at 12-weeks post-operative will be compared between patients who receive tele-rehab-supported PT (virtual group) versus traditional home and/or clinic-based PT (control group) for TKR. The primary cost comparisons will be done using an analysis of variance (ANOVA) method for continuous variables if (1) the dependent variable is normally distributed or (2) can be normalized using a transformation such as the logarithm or square root. The underlying assumptions of the statistical test procedure will be verified through non-normality tests and plots. If there is strong evidence that the assumptions are not met or cannot be met with an appropriate distribution, the nonparametric Wilcoxon Rank sum test will be used.

The total health service use costs at 12-weeks post-operative will be the primary effectiveness endpoint for this study. This will be calculated using a fee-for-service model and assigned costs. Tele-health for rehabilitation services was not a reimbursable service at the start of the trial, and thus a total intervention cost, including direct and indirect time with physical therapy and any in-person visits, is assigned using the following units and costs:

Healthcare Encounter	Unit	Cost
Intervention	Total (all interactions)	\$600
Home health PT	<5 visits (cost per visit) ≥5 visits (single cost per 60-day episode)	\$133 \$2,325
Outpatient clinic PT	Single visit	\$90
PT call/email	Single interaction	n/a
Doctor's office	Single visit	\$150
Doctor's office call/email	Single interaction	n/a
Urgent care or ER visit	Single visit	\$250
Re-hospitalization	Full length of one inpatient stay	\$7,825
Inpatient rehab facility	Full length of stay	\$10,720
Skilled nursing facility	Full length of stay	\$6,510

Intervention Group Patients: Total costs will be calculated as the assigned cost of the intervention plus assigned costs for any reported doctor's office visits, urgent care or ER visits, re-hospitalizations, and inpatient rehabilitation or skilled nursing facility stays in the 12 weeks following discharge from the surgical hospital stay. The formula is as follows:

Cost = intervention cost + (# of doctors office visits * \$150) + (# of ER/UC visits * \$250) + (# of re-hospitalizations * \$7,825) + (# of skilled nursing facility stays * \$6,510) + (# of inpatient rehabilitation facility stays * \$10,720)

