9.11.1 Effectiveness hypothesis (Non-Inferiority Test)

The tele-rehab intervention will be non-inferior to traditional PT at 6 weeks (differences between groups <5% for clinical and patient-reported outcomes) and 12 weeks (difference <5% patient-reported outcomes). The secondary objectives are to compare tele-rehab-supported PT and traditional PT on patient-centered outcomes as follows:

- 6 Weeks:
 - KOOS: Total score based on a normalized scale of 0-100 (worst to best). The minimal perceptible clinical improvement difference (MCID) for non-inferiority that we will use is 10 points.
 - ROM: This is reported to reflect both extension (lower) and flexion (upper) range of motion. An MCID is not available and based on recent literature we will use 6.3 degrees for extension and 9.6 degrees for flexion.
 - Gait Speed (m/sec): MCID is 0.1 m/s
- 12 Weeks:
 - KOOS: The minimal perceptible clinical improvement difference (MCID) for non-inferiority will be 10 points.

Analyses for each endpoint will be similar to those considered in Section 9.10 for the primary cost endpoint, except the tests will be one-sided for non-inferiority. A one-sided 95% confidence interval for the mean difference between intervention groups will be completed using parametric methods if possible; otherwise, the median difference will be utilized.

Non-inferiority will be determined if the upper bound of the difference indicative of treatment benefit in the control group is less than the MCID for each endpoint. No adjustment for multiple comparisons is necessary since all tests must be significant to determine non-inferiority (intersection-union multiple testing rule) for effectiveness.

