9.11.2 Safety hypothesis (Non-Inferiority Test)

The tele-rehab intervention will be non-inferior to traditional PT at 12 weeks using the following endpoints at 12 weeks:

- Pain: The minimal perceptible clinical improvement difference (MCID) for non-inferiority will be 1.7
- Re-hospitalizations: The total number of re-hospitalizations will differ by no more than 1.
- Falls: The percentage of subjects reporting any fall from index hospital discharge until 12 weeks postoperative will differ by no more than 10% (reported at 6 and 12 weeks as a categorical yes/no response).

A one-sided 95% confidence interval for the mean difference between intervention groups will be completed using parametric methods if possible; otherwise, the median difference will be utilized. Non-inferiority will be determined if the upper bound of the difference indicative of a treatment benefit in the control group is less than the MCID for each endpoint. No adjustment for multiple comparisons is necessary since all tests must be significant to determine non-inferiority (intersection-union multiple testing rule) for the safety hypothesis.

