9.12 Other Exploratory Analyses

The final objectives (exploratory analyses) are to determine if superiority between PT methods exist for the endpoints primarily tested for non-inferiority, determine whether individual patient characteristics are associated with differential improvement from 6 to 12 weeks assessed by patient-reported outcomes, and to determine the cost for the VERA system such that the cost between the control group and intervention groups is cost-neutral, assuming that the intervention group is determined to cost less. The secondary endpoints that will be considered are detailed in Sections 7.2-7.4.

An appropriate regression model may be considered for the primary cost endpoint to adjust for baseline variables found to be imbalanced or to assess the influence of site on treatment effects. This will be done by adding a fixed-effect main site effect and interaction term between randomization strata (site) and treatment in a generalized linear model. Assuming the average cost for the intervention group is lower than the control group, we will also determine the cost for the VERA system such that the cost difference between the control group and the intervention group is cost-neutral.

If the endpoints tested for non-inferiority between PT methods are found to be non-inferior, then additional analyses to control for baseline covariates or site effects may be done using methods previously described to determine if the PT group is superior to the control group after adjustment.

To determine whether individual patient characteristics are associated with differential improvement, we will evaluate the change over time (0-6, 0-12 and/or 6-12 weeks) for endpoints measured at multiple time points using parametric or non-parametric methods previously discussed. When both 6 and 12-week assessment are made, the Sidak alpha-correction method will be used to correct for multiple comparisons. The correction method is given by $1-(1-\alpha)^{1/k}$, where k is the number of comparisons considered. If adjustments for baseline covariates are necessary, generalized repeated measures models will be used to assess main effects of intervention group and time, as well as the interaction between time and intervention groups.

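### Site and scheduled baseline values are left out of the primary and non-inferiority tests: the tests are valid, but some precision is unused, mainly for gait speed and KOOS

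*SAP*

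**What the plan says.** **Design.** SAP 6.1: "Subjects will be randomized in a 1:1 ratio, stratified by site"; SAP 7.5 and 9.3 agree. Protocol Table 1 and sections 4.2.3 and 4.2.4 schedule KOOS, PROMIS, prior falls and hospitalizations, and 10 m gait speed at baseline. SAP 9.6.2 marks gait speed as summarized only where collected. Range of motion is first measured at 6 weeks, and no baseline cost is collected.

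**Primary test.** SAP 9.10 opens with "The primary cost comparisons will be done using an analysis of variance (ANOVA) method for continuous variables" but names no factor beyond treatment group. It then specifies "The primary statistical method for the hypothesis test will be t-test, and the mean difference between groups" with a 95% CI, on n_T + n_C - 2 degrees of freedom. An unequal-variance version and a Wilcoxon fallback follow. The power section matches: "The sample size estimates were made assuming a two-sample t-test with equal variance and a significance level of 0.05".

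**Non-inferiority tests.** SAP 9.11.1: "Analyses for each endpoint will be similar to those considered in Section 9.10 for the primary cost endpoint", made one-sided. SAP 9.11.2 adds no covariate for pain, re-hospitalizations or falls ("Falls: The percentage of subjects reporting any fall from index hospital discharge until 12 weeks postoperative will differ by no more than 10" percentage points).

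**Where site and baseline do appear.** SAP 9.3: "Exploratory analyses will include assessing the influence of site on treatment effects for both the primary and secondary endpoints", through a site effect and a site-by-treatment interaction. That analysis is planned, but as exploratory. Baseline adjustment is optional. SAP 9.12 says "An appropriate regression model may be considered for the primary cost endpoint to adjust for baseline variables found to be imbalanced", and allows adjusted superiority analyses once non-inferiority has been shown.

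**Missing data.** SAP 9 and 9.4 rule out imputation.

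**The concern.** If site predicts outcome, a stratified design analysed without site leaves between-site variation in the error term. A baseline that correlates with the outcome can reduce the error further at no data cost. The effectiveness claim in 9.11.1 requires every test to pass, so the endpoint with the least precision relative to its margin limits the joint claim. The documents give no SD and no power for any non-inferiority endpoint.

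Two matters need settling if adjustment is used, including the optional adjustment already allowed in 9.12. First, there is no rule for patients without a baseline. Second, choosing cost covariates by observed imbalance leaves the adjusted model to be selected after data are seen.

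**Working it through.** **1. The plan's own figure.** Two-sided 0.05 t-test, 150 per arm, noncentral t with 298 df: power is 81.3% at effect size 0.33 and 80.0% at 0.3245, the value implied by the dollar table ($486.80 / $1,500). The stated 80% reproduces.

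**2. Validity.** A simulation used 6 sites of 50, blocked within site, under the null, with site explaining 5-10% of variance. The unadjusted t-test rejected about 4.0-4.1% of the time and the site-adjusted test 4.7-5.1%, against a nominal 5%. With site effects in one arm only, the unadjusted test rejected 4.3-4.7%. It is therefore valid, and mildly conservative when arms are balanced within site and site predicts outcome.

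**3. Non-inferiority power.** Inputs from SAP 9.11.1: margins of 0.1 m/s (gait) and 10 points (KOOS), one-sided 0.05. From SAP 9.9: 150 per arm. Assumed: true difference 0, the SD, and baseline-outcome correlation r = 0.3 to 0.5. When a fraction f of patients has a baseline and all patients are kept:

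SE = SD × √(2/150) × √(1 - f·r²)

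- f = 1: √(1 - 0.09) = 0.954 and √(1 - 0.25) = 0.866, an SE cut of 5-13%.
- f = 0.5: √(1 - 0.045) = 0.977 and √(1 - 0.125) = 0.935, an SE cut of 2-6%.

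Example, gait SD 0.30: the unadjusted SE is 0.30 × 0.1155 = 0.0346. It becomes 0.0330 (r = 0.3) or 0.0300 (r = 0.5).

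| Endpoint, assumed SD | Unadjusted | Adjusted, f = 1 | Adjusted, f = 0.5 |
|---|---|---|---|
| Gait 0.20 | 99.6% | 99.8-100% | 99.7-99.9% |
| Gait 0.25 | 96.5% | 97.6-99.1% | 97.1-98.0% |
| Gait 0.30 | 89.2% | 91.5-95.4% | 90.4-92.4% |
| Gait 0.35 | 79.5% | 82.7-88.6% | 81.1-84.0% |
| KOOS 20 | 99.6% | 99.8-100% | not computed |
| KOOS 25 | 96.5% | 97.6-99.1% | not computed |

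A simulation of mean-fill with a missing indicator plus site (gait SD 0.30, site R² 0.02) gave power of 91.8-95.5% at f = 1 and 91.7-92.8% at f = 0.5. Size at the margin was 4.6-5.1%.

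**4. If patients without a baseline are dropped.** Relative variance is (1 - r²)/f, so adjustment gains only if f exceeds 1 - r², which is 91% at r = 0.3 and 75% at r = 0.5. At f = 0.5 (75 per arm), gait SD 0.30, power is 68.6-75.8% against 89.2% unadjusted.

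**5. Falls.** With the 10-point margin and a normal approximation, unadjusted power is 99/89/78/70% at assumed fall rates of 5/10/15/20%. In simulation, site cut the SE by 0.2-2.1% and site plus prior falls by 0.8-3.9%. That adds at most about 2 points of power. Re-hospitalizations were not simulated separately; little gain is expected for an infrequent count.

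**6. Cost.** Simulation with the SAP unit costs and an assumed between-site SD of 0.15-0.35 in home-health share. Site cut the SE by 0.1-1.3% when 2-8% of patients were re-hospitalized, and by 1.5-6.2% only if nobody was. A 1.3% cut corresponds to R² = 1 - 0.987² = 0.026. At R² = 0.02 primary power moves from 80.0% to 80.8%, and at 0.05 to 82.0%.

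**7. Timing and instrument of the baseline.** Protocol 4.2.1 allows randomization before or after the patient-reported baseline is completed, and SAP 7.5 says patients are not blinded. If knowing the arm shifts the baseline by d, a baseline-adjusted effect is biased by about r × d. For an assumed 5-point KOOS shift and r = 0.5 this is 0.5 × 5 = 2.5 points, a quarter of the margin. The unadjusted test has no such bias. SAP 9.8.2 also allows KOOS junior at 6 weeks, whereas the scheduled baseline is KOOS.

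**The case against.** The strongest case against is that nothing here is wrong. The unadjusted test controls type I error, its stated power reproduces, and it is the method the sample size was set for. A site model is already planned in 9.3. The gain for the primary endpoint is negligible, KOOS may already have ample power, and range of motion, which has no baseline, could be the limiting endpoint. No joint power was calculated. All of this stands, and it keeps the point to one of efficiency.

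The objection that baseline adjustment is not automatically free also stands. KOOS and PROMIS pain may be recorded after the patient knows the arm, so adjusting for them without a timing condition could replace an unbiased comparison with a biased one. No such shift is documented; the 2.5 points is an illustration.

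A reader might infer that omitting the stratification factor invalidates the tests or inflates alpha. The direction is the opposite: at most they are mildly conservative. Nor must site act in both arms for that conservatism to arise (step 2). A reader might also infer that the SAP ignores site. It does not; it makes site exploratory.

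What the objection does not remove is that the stratum and some baselines will be in hand, and that gait speed could lack power at a plausible SD.

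**Conclusion.** The point holds as an improvement worth making, not as an error. Its weight is on gait speed and KOOS: a 5-13% smaller SE under correlations of 0.3-0.5 with complete baselines, and 2-6% if half are collected. Gait-speed power gains about 2 to 6 points at an assumed SD of 0.30, and almost nothing at 0.20. KOOS behaves the same way at the same ratio of margin to SD. For cost, falls and re-hospitalizations the gain from site is very small.

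Every SD, correlation, fall rate and site effect is an assumption, and power is at true equality with 150 per arm. The gain applies to the parametric route. The conservatism depends on balance within site; section 9.5 (Randomization Form) and a short part of 9.10 were not in the text available for this check. The documents do not support any claim that the planned tests are invalid or that the primary comparison loses its stated power.

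**What to change.** **SAP 9.11.** Prespecify a linear model with treatment, site and the baseline value for gait speed and for KOOS, and treatment plus site for range of motion. Use a baseline only if it was recorded before randomization; treat later values, including discharge values, as a missing baseline. Apply the same condition to PROMIS pain if it is used. For 6-week KOOS, compute the baseline score on the same version as the outcome. State that falls and re-hospitalizations stay unadjusted, or adjust them for site.

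**SAP 9.4.** State that patients without a usable baseline covariate are kept, by mean-fill or a missing indicator, with the unadjusted test as a sensitivity analysis. State that outcomes remain unimputed.

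**SAP 9.10 (optional).** Site may be added to the cost ANOVA for a small gain. If it is, state how unequal variances are handled (for example, robust SEs), make the fallback a site-stratified rank-sum test, and report the unadjusted test as well.

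**SAP 9.12.** Name the covariates of any adjusted cost model in advance instead of selecting those found imbalanced.

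**Cost.** No new data or patients. It takes a model statement per endpoint, a short rule in 9.4 and a phrase in 9.12, all fixed before unblinded analysis. The downside is slightly more analysis work, a check of baseline dates against randomization, and a benefit that depends on baseline timing and completeness.

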9 GENERAL METHODOLOGY

Descriptive statistics will be grouped into three categories: Tele-rehab PT, Traditional PT, and Overall. Continuous variables will be summarized by the number of observations and the mean, standard deviation, median, minimum, and maximum values. For categorical data, the counts, denominators and percent per category will be presented within non-missing observations. Subjects with a missing value for a variable will not be included in the calculation for that variable. All continuous data will be summarized with one more significant digit than in the dataset. Percentages will be rounded to one digit to the right of the decimal. Subjects with missing categorical data will not be included in calculations of percentages for that variable unless otherwise specified. No imputation will be made for missing values. Both the frequency and the associated denominator will be shown to facilitate review of missing categorical data. Categorical responses of "Unknown" will be set to missing.

It is anticipated that both the 6- and 12-week follow-up calls will not occur exactly at 6 and 12 weeks post-op, respectively, for every patient. However, the DCRI Call Center is instructed to contact subjects as close as possible to the appropriate time since postoperative discharge date. Data needed for the primary endpoint will be prioritized if patients agree to spend only a limited time on the follow-up call.

All statistical tests will be one-sided (non-inferiority) or two-sided (superiority) with a significance level of 0.05, unless otherwise documented. Tests for differences between treatment groups for endpoints that are not protocol-specified may be performed. Unless otherwise stated, continuous variables will be compared between groups with two-sample student t-test or with Wilcoxon's rank-sum test depending on normality assumptions.

When it is necessary to detect differences between groups, unless it is stated otherwise, categorical values will be compared using the chi-square test or Fisher's exact test. The chi-square test will be used when all cells in the table of the categorical comparison have an expected value of 5 or above. Otherwise, a Fisher's exact test will be performed.

All tables will be presented with summary statistics overall and by treatment group unless otherwise specified.

All analyses will be completed using SAS version 9.4 or higher.

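### The only rejection region written for the primary t-test is lower-tail, against a declared two-sided test, and the condition for using that branch is defective as worded

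*SAP*

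**What the plan says.** SAP 9.10 states the null as equal mean costs and the alternative as unequal mean costs. In words: "The alternative hypothesis is that a treatment difference exists between patients who receive tele-rehab-supported PT versus traditional home and/or clinic-based PT". It explains the choice: "The test is two-sided even though we are more interested in determining that the intervention group is superior to the control group", the purpose being "to allow for a possible negative significant difference". The mean difference is to be reported with a 95% CI. SAP 9 sets the general rule: "All statistical tests will be one-sided (non-inferiority) or two-sided (superiority) with a significance level of 0.05, unless otherwise documented".

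SAP 9.10 then describes a folded F-test of the two variances and a branch:

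- **Equal-variance branch.** It opens with "If there is not strong statistical evidence to say that the variances of the two samples are different", and a parenthesis spells this out as "insignificant F-test and 4-fold variance difference". The alternative then "will be concluded when the associated t-test statistic assuming equal variance is less than the 2.5th percentile" of the t distribution with the pooled degrees of freedom.
- **Other branch.** The t-test is computed assuming unequal variances. No rejection region is given.

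The sign of t is not defined, and neither is the level of the F-test. If normality cannot be achieved, a Wilcoxon rank-sum test replaces the t-test.

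**The concern.** This is the decision rule for the primary endpoint, and it has two separate faults.

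First, the hypotheses, the stated reason for a two-sided test and the general rule in SAP 9 all require rejection in both tails. The written region covers one. Taking t as virtual minus control, it is the tail in which tele-rehab is cheaper. The outcome that the two-sided test was chosen to allow for is the one the written rule leaves out.

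Second, the condition for entering that branch joins a non-significant F-test to a 4-fold variance difference. At the planned size these exclude each other, so a programmer cannot tell from the text which form of the t-test is primary.

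At stake is a primary conclusion that could conflict with its own confidence interval, and a choice of rule that would have to be settled after the data are unblinded. SAP 9.11.1 carries the 9.10 methods over to the non-inferiority effectiveness endpoints, so the unclear variance condition carries over too.

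**Working it through.** **Inputs.** 150 per group, effect size about 0.33 and at least 80% power (SAP 9.9; Protocol 5.1); two-sample t-test with equal variance at 0.05 (same sections); 1:1 allocation (SAP 6.1). Assumed, because the SAP does not say: normal data, and a 5% level for the F-test.

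**1. Reproduce the plan's power.** The standard error of the mean difference in SD units is sqrt(2/150) = 0.1155. Degrees of freedom are 150 + 150 − 2 = 298, and the critical value is 1.968. The noncentrality at 0.33 SD is 0.33 / 0.1155 = 2.858. Noncentral-t power is 0.813 at 0.33 and 0.7999 at 0.3245. Seven rows of the Protocol 5.1 table were checked (for example 0.8023 at 0.3255 and 0.8209 at 0.3335), and all agree to within 0.0001 with a two-sided 5% test. A one-sided 5% test would give 0.887 at 0.33 (normal approximation). The design was therefore sized for a two-sided test.

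**2. The written region (t < −1.968 only), with t as virtual minus control.**

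| True difference | Lower tail only | Two-sided |
|---|---|---|
| −0.33 SD (tele-rehab cheaper) | 0.813 | 0.813 |
| 0 | 0.025 | 0.050 |
| +0.33 SD (tele-rehab costlier) | about 8e-7 | 0.813 |

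**3. Conflict with the interval.** The half-width of the 95% CI is 1.968 × 0.1155 = 0.227 SD. An observed difference of +0.33 SD gives 0.103 to 0.557 SD, which excludes zero, while the written rule does not conclude a difference. In dollars, take the SAP 9.9 row with an SD of $1,500 and a difference of $486.80, here against tele-rehab. The interval is 486.80 ± 0.2272 × 1,500, or about $146 to $828.

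**4. The branch condition.** The two-sided 5% critical value of F on 149 and 149 df is 1.380. A variance ratio of 4 has p = 3.9e-16. Three readings are possible:

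- *Literal: non-significant and at least 4-fold.* Met in 0 of 200,000 simulated trials at 150 per arm. It is possible only at 10 or fewer per arm (critical F is 4.03 at 10 and 3.72 at 11).
- *Non-significant and less than 4-fold.* Any non-significant ratio is already below 1.38, so the 4-fold clause adds nothing. The pooled branch is reached in about 95% of trials when true variances are equal, 80% at a true ratio of 1.2, 31% at 1.5 and 1% at 2.0.
- *Unequal-variance test only if the F-test is significant and the ratio is at least 4.* Observed ratios from 1.38 to 4 then go to the pooled test, where the second reading sends them to the other branch.

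**5. How much the branch matters once both tails are stated.** With exactly equal arms the pooled and unequal-variance statistics are the same number, because both denominators equal sqrt((S_T² + S_C²)/n). Only the degrees of freedom differ: 149 × (1 + r)² / (1 + r²) for an observed variance ratio r. At r = 1 this is 298 (critical t 1.968); at r = 4 it is 149 × 25 / 17 = 219 (critical t 1.971). With equal true variances, 200,000 simulated trials at 0.33 SD gave power of 0.812 for both tests.

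**The case against.** The plan's intent is plainly two-sided. The hypotheses, the explanatory sentence, the general rule in SAP 9 and the 95% CI all say so, and Protocol 5.2 uses a tail-neutral p-value criterion. The 2.5th percentile is itself the half-alpha cut-off of a two-sided 5% test, so the sentence may simply give the tail of interest and omit its mirror image. The lead-in to the variance condition likewise suggests that the words *less than* were dropped. Even read literally, the region is conservative: it cannot create a false claim of saving, and it costs no power for the hypothesised benefit. Skewed costs may also go to the Wilcoxon test, which carries no lower-tail wording. All of this stands, and it limits the severity.

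A reader might infer that the plan both cannot detect a costlier intervention and never permits the pooled test. The documents do not support the two together. The lower-tail rule belongs to the equal-variance branch alone. If the literal condition makes that branch unreachable, the unequal-variance test always applies. It has no stated tail, falls under the two-sided rule in SAP 9, and can find tele-rehab costlier. If the branch is reachable, the pooled test is permitted.

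The objection does not remove the fault. Under the likely intended reading, the pooled branch is entered routinely when variances are similar, and its written region contradicts the hypothesis it tests. Under the literal reading, the only critical value in the section belongs to a test that is never run.

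**Conclusion.** The concern holds as an internal contradiction in the primary decision rule, of moderate severity. Where the equal-variance branch applies and is followed to the letter, the test has a type I error of 2.5% rather than 5%. It would almost never conclude a difference if tele-rehab were costlier by 0.33 SD (about 8e-7 against 0.813), even when the 95% CI excludes zero. The variance condition is either impossible to meet or partly redundant, depending on the reading, so which t-test is primary is not fixed.

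The consequence is confined to how an adverse cost result would be concluded and to which variance form is used. Power for the hypothesised saving (0.813) and the sample size are untouched. With 1:1 arms the choice of variance form barely moves the critical value, so the missing tail is the more consequential fault.

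The figures assume normal data, 150 analysed per arm, t taken as virtual minus control, and a 5% F-test. Of these, only the planned 150 per group is stated in the SAP.

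**What to change.** In SAP 9.10:

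1. Define t as virtual minus control, and reject the null when |t| exceeds the 97.5th percentile of the relevant t distribution, whichever variance form is used. This restores a 5% type I error and gives power of 0.813 at 0.33 SD in either direction.
2. Preferably, use the unequal-variance (Welch/Satterthwaite) t-test throughout and delete the folded-F and 4-fold pre-test. Unequal variances are plausible: tele-rehab carries a flat $600 with no per-visit PT term, while the cost table prices home and clinic PT by visit or episode.
3. If the pre-test is kept, state the F-test level, write less than 4-fold, and say whether both criteria or either one is needed. This is the minimum repair; the contradiction does not by itself require dropping the pre-test.

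The cost is about two sentences, made before database lock. Sample size does not change, and the power loss from the unequal-variance test is negligible with 1:1 arms.
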